1. LIST OF ABBREVIATIONS

BI	Boehringer Ingelheim
CI	Confidence Interval
DMRP	Data management and review plan
HDPS	High dimensional propensity score
IHD	Instant Health Data
IQR	Interquartile range
NIS	Non-interventional study
SEAP	Statistical and epidemiological analysis plan
SGLT2i	Sodium glucose co-transporter-2 inhibitor
T2DM	Type 2 diabetes mellitus
US	United States

3. PURPOSE AND SCOPE

SEAP reviewers are expected to be familiar with the NIS protocol entitled “Post-authorization safety study (PASS) to assess the risk of acute pancreatitis in type 2 diabetes mellitus (T2DM) patients newly initiating empagliflozin compared to other oral non-incretin/non-sodium glucose co-transporter-2 inhibitors (SGLT2)-based glucose lowering agents”, version 1.0 dated 29 November 2021 unless otherwise stated.

The SEAP addresses the details of the implementation of this study. In the SEAP, you can find the detailed operational definitions on how to identify each of the index medication cohorts, detailed data analysis plan such as the propensity score matching, meta-analysis, and Main analysis plan. In addition, the study covariates are captured in the [Annex 3](#).

4. AMENDMENTS AND UPDATES

None.

5. RESEARCH QUESTION AND OBJECTIVE

This non-interventional cohort study using data from two large United States claims databases will describe the risk of acute pancreatitis among patients with type 2 diabetes mellitus (T2DM) initiating empagliflozin between from 1 August 2014 to the latest data-cut available in Marketscan (30 September 2020) and Optum (31 March 2021).

Primary Objective:

- To compare the incidence rate of acute pancreatitis in T2DM patients initiating empagliflozin to new users of other oral non-incretin/non-SGLT2i-containing glucose lowering drugs between 1 August 2014 and the latest data-cut available in Marketscan (30 September 2020) and Optum (31 March 2021).

6. RESEARCH METHODS

6.1 STUDY DESIGN

Please see the study protocol.

6.2 SETTING

Please see the study protocol.

6.2.1 Study period

The patient selection period will be from 01 August 2014 to the latest data-cut available in Marketscan (30 September 2020) and Optum (31 March 2021). Patients will be selected into the study at any time during this period once they fulfil the study eligibility criteria.

6.2.2 Baseline period (lookback period)

Patients are required to have at least 6 months of continuous registration in the database prior to initiation of empagliflozin or a comparator drug. The look-back period is defined as 6 months prior to the index date and including the index date. The look-back period was specified to confirm new medication use (i.e., having a first prescription claim for empagliflozin or other oral non-incretin/non-SGLT2i-based glucose lowering agents without use of these medications in the prior 6 months) and describe baseline parameters, such as prior medical history and medications.

6.2.3 Follow up

Follow up starts at the day after the index date until the first qualifying event has been met (see table 2 and 3 of the study protocol).

6.3 STUDY POPULATION

Please see the study protocol for the details.

Codes to select study population are listed in [Annex 1](#).

One of the risk factors of acute pancreatitis is severity of diabetes and diabetes duration [[R10-6620](#), [R10-2088](#)]. In the Optum and Marketscan databases duration of diabetes can not be measured for all patients, therefore chronic use of insulin at baseline was selected as an exclusion criterion to remove severe cases of diabetes who are already at higher risk of developing acute pancreatitis. We defined 60 (or more) days of continuous exposure as chronic use of insulin for the exclusion criteria.

The operational steps are as follows:

Insulin prescriptions will be extracted during the 6 months baseline period according to insulin medication codes listed in [Annex 2](#). Despite the variations in package size and dosing schedule, a majority of insulin prescriptions are dispensed with 30 days' supply [[R21-4257](#), [R21-4258](#)].

The continuous exposure episode of insulin is constructed by linking insulin prescriptions with allowed less or equal 30 gap days [[R21-0580](#)]. If any of continuous exposure episodes have 60 or more than 60 days duration, this will be considered as chronic use of insulin and this patient will be excluded from the cohort.

6.4 STUDY VISITS

Not applicable.

7. VARIABLES

Study variables are explained the study protocol [section 9.3](#). you can find attritional operational definitions below:

7.1 EXPOSURES

Please check section 9.3.1 of the study protocol.

7.1.1 Operational definitions on how to identify each of the index medication cohorts:

For index medication determination, we first select all patients with any of Empagliflozin, TZD, SU and Metformin prescriptions within study period. Then we evaluate index drug for each patient following this order: Empagliflozin → TZD → SU → Metformin. Therefore, each patient will be classified into one of index cohorts only once. The details for Empagliflozin initiators are provided below and all other drugs follow the same approach.

Empagliflozin initiators:

1. Between Aug 2014 and latest data cut we will choose all Empagliflozin new users. The date of first Empagliflozin prescription will be selected as index date. New users should not have any prescriptions for Empagliflozin in 6 months prior to the index date.
2. In the next step we will check which of the Empagliflozin initiators use metformin, or SU in the 6-month baseline period

[figure not shown]

Figure 1

Diagram for Mono, Combo or Triple groups creations

Code list for exposure variables is available in [Annex 2](#).

The index date in both groups will be the date of prescription of empagliflozin or other hypoglycaemic therapies (index medication), and the planned study follow-up period starts at the day after index date.

Proprietary confidential information © 2022 Boehringer Ingelheim International GmbH or one or more of its affiliated companies

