- The date of discontinuation of index medication (defined as the date of the last date of last dispensing + days supply + grace period). The grace period is a time period after exposure end during which observed outcomes are still attributed to the exposure. Grace period varies according to the specific outcome. In this study, for acute pancreatitis, we have 30 days [[c18659315-02](#)] grace period in the main analysis and 90 days in the sensitivity analysis [[R18-1760](#), [RRA-21430](#), [P20-07536](#)].
- The date of switch of index medication to another hypoglycaemic agent (see [section 9.7.1](#) and SEAP)
- The date of addition of incretin-based therapy (with continuation of index therapy)
- The date of addition of SGLT2i (with continuation of index therapy)
- The date of addition of insulin (with continuation of index therapy)
- The date of addition of the within treatment line comparator index drug (with continuation of index therapy)

All definitions can be found in section 9.7.1. All codes used to define exposure variables are listed in Appendix 4.

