### **9.7.1 Definitions**

- Index date: Date of the first recorded claim for a qualifying prescription of an index medication as a new user.

- Follow-up: Starts from the day after the index date until the first qualifying event has been met (see [Table 2](#) and [3](#)).
- Look-back period: Patients are required to have at least 6 months of continuous registration in the database prior to initiation of an index medication. The look-back period is defined as 6 months prior to the index date and including the index date. The look-back period was specified to confirm new medication use (i.e. having a first prescription claim for empagliflozin or other oral non- incretin/non-SGLT2i-containing hypoglycaemic without use of these medications in the prior 6 months) and describe baseline parameters, such as prior medical history and medications.
- Grace period: 30 days in main analysis [[c18659315-02](#)] and 90 days [[R18-1760](#), [RRA-21430](#), [P20-07536](#)] in sensitivity analysis.

Table 2 Definitions for study end date

Reason for End of Study or censoring (earliest date of options below)	Definition for End Date
Acute pancreatitis event	Date of the first acute pancreatitis using ICD9 or ICD10 codes
Switch of index medication to another hypoglycaemic agent; see Table 3	Last date of known prescription coverage (date of last prescription fill plus days' supply minus one day) and a grace period equal to 30 days. Exposure time will not extend past the date of the first prescription claim for the newly prescribed agent*
Addition of incretin-based therapy (with continuation of index therapy)	Date of the prescription claim for the added incretin therapy
Addition of SGLT2i (with continuation of index therapy)	Date of the prescription claim for the added SGLT2i therapy
Addition of insulin (with continuation of index therapy)	Date of the prescription claim for the added insulin therapy
Addition of the within treatment line comparator index drug; see Table 3 (with continuation of index therapy)	Date of the prescription claim for the added treatment line comparator index drug
Discontinuation of index drug	Last date of known prescription coverage (date of last prescription fill plus days' supply minus one day) and a grace period equal to 30 days*
End of study data	Date of death#, Date of end of registration, Date of Study End

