\*The last date of known coverage may also be extended further to account for overlap periods – when a prescription is refilled before the previous supply was considered exhausted. Gaps between coverage and prescription refills that are less than the duration of each patient's respective grace period will be considered continuous exposure time.

#It is not typically possible to ascertain all deaths that occur in studies based on administrative claims data.

Discontinuation, addition, and switching are defined in the SEAP. Considerations for the follow up time and censoring after switching or addition are presented in Table 3.

Index drug for the monotherapy are empagliflozin and metformin, for the dual therapy empagliflozin and SU, and for the triple therapy cohort empagliflozin and TZD.

Table 3 Considerations for switching or adding during the follow-up period

Treatment Line	Index Drug	Can Add (i.e. do not censor)	Cannot Add (i.e. censor at switch/addition)
Monotherapy	Empagliflozin	SU, TZD, and medications not mentioned in the next column	Metformin, incretins*, other SGLT2i, Insulin
	Metformin	SU, TZD, and medications not mentioned in the next column	Any SGLT2i, incretins*, Insulin
Dual Therapy	Empagliflozin	TZD, and medications not mentioned in the next column	SU, incretins*, other SGLT2i, Insulin
	SU	TZD, and medications not mentioned in the next column	Any SGLT2i, incretins*, Insulin
Triple Therapy	Empagliflozin	Medications not mentioned in the next column	TZD, incretins*, other SGLT2i, Insulin
	TZD	Medications not mentioned in the next column	Any SGLT2i, incretins*, Insulin

\*Incretins = DPP-4i or GLP-1 RA.

In the dual therapy and triple therapy cohorts, if patients discontinue or switch medications other than index medication (e.g. metformin in the dual therapy cohort, and SU or metformin in the triple therapy cohort) they will not be censored; however, in the sensitivity analysis, this will be assessed by censoring those patients. Definitions for discontinuation, switch, and addition are mentioned in the SEAP.

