For patients who add an incretin-based therapy, SGLT2i, or a within treatment line comparator index drug, their data will be censored on the date of the prescription claim for the added medication.

Patients with chronic use of insulin at baseline (see SEAP for definition) in the outpatient setting during the follow-up period will be censored from the study.

From a feasibility assessment conducted in November 2021, it is known that there are not enough study participants in the Optum and MarketScan database in each therapy line and the dual-therapy cohort was reported with the highest number of empagliflozin initiators. Therefore, a meta-analysis of the dual therapy cohorts including the data from the Marketscan MarketScan and Optum databases will be the main analysis of this study

Meta-analysis of different treatment line cohorts with the different comparators (first, second and third line) will not be conducted in this study as patients in these 3 cohorts will likely have very different profiles including different disease stages, and results would be difficult to interpret.

The incidence rates (per 1000 PY) and corresponding 95% confidence intervals (CI) of acute pancreatitis during the follow-up time will be calculated in each exposure group of interest in the unmatched and PS-matched cohorts.

All results will be presented for each database separately but if there is not enough sample size in each treatment line cohort in each database, after evaluating potential heterogeneity, meta-analysis techniques will be used to pool the 2 treatment line cohorts of the 2 databases. Descriptive tables and all parameter estimates from the main and all sensitivity analyses will be pooled using meta-analytic methods assuming a fixed effects model, to avoid potential biases associated with random effects pooling in the context of few databases [R17-1410].

Cox proportional hazards regression models based on time-to first acute pancreatitis event will be used to estimate hazard ratios (HR) and 95% CIs for each treatment line comparison of interest (in each database or in case of limited sample size a meta-analysis of 2 databases) in the unmatched and PS-matched cohorts. Proportionality hazard assumption will be checked using the log rank test.

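### As worded, SAP 7.1.1 lets drugs started later decide who enters the sulfonylurea arm, against the protocol's index-date and censoring rules

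*SAP*

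**What the plan says.** SAP 7.1.1 builds the cohorts in three moves.

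- Selection: "we first select all patients with any of Empagliflozin, TZD, SU and Metformin prescriptions within study period".
- Assignment: "Then we evaluate index drug for each patient following this order: Empagliflozin → TZD → SU → Metformin".
- Exclusivity: "Therefore, each patient will be classified into one of index cohorts only once".

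Step 1 for empagliflozin reads "Between Aug 2014 and latest data cut we will choose all Empagliflozin new users". The only new-user condition given there is no empagliflozin in the preceding 6 months. Nothing refers to an earlier SU start, and the other drugs are to follow the same approach.

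The protocol works by date. Section 9.7.1 defines the index date as "Date of the first recorded claim for a qualifying prescription of an index medication as a new user". Later starts are dealt with during follow-up. For additions of an incretin-based drug, section 9.7.3 continues: "SGLT2i, or a within treatment line comparator index drug, their data will be censored on the date of the prescription claim". In the dual-therapy rows of Table 3 (section 9.7.1), an SU patient is censored at any SGLT2 inhibitor, while the list of drugs that may be added without censoring is "TZD, and medications not mentioned in the next column". SAP 7.1.3 likewise treats the comparator as a censoring event and allows other non-incretin, non-SGLT2 agents to be added.

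**The concern.** Under the SAP wording, a patient on metformin who starts an SU and later becomes a new user of empagliflozin or a TZD is not an SU initiator. If SU was used in the 6 months before the empagliflozin start, or the TZD start is on metformin plus SU, the patient appears to move to the triple-therapy cohort. Protocol 9.2.2 says that cohort cannot be assessed, so the patient's SU time and any event leave the analysis.

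The rule is one-sided. An empagliflozin initiator who later adds SU is kept and censored, and one who adds a TZD is kept uncensored.

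This is the comparator arm of the only powered analysis (protocol 9.5). Conditioning SU entry on later starts makes the SU rate of acute pancreatitis (AP) depend on how AP relates to those starts:

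- **No bias** if later starts are unrelated to AP.
- **Hazard ratio (HR) too low** (a false finding of safety) if AP makes a later start less likely. The same holds if AP cases who fail the later drug's prior-pancreatitis exclusion fall back into the SU arm. Neither document says whether they do.
- **HR too high** if later starts are more likely after AP, or if later starters carry a higher AP risk.

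Propensity matching uses baseline covariates. It cannot undo a change in starts after AP, and it removes selection on risk only as far as those covariates capture it. The 12-month intention-to-treat analysis (protocol 9.7.6), as described, does not rebuild the cohort. Quality control under SAP section 11 checks the analysis against the SAP, so it would not flag the rule.

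**Working it through.** **1. The passages applied to one patient.** A metformin patient starts an SU, and two years later, still on SU, starts a second drug as a new user.

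| Second drug | Protocol 9.7.1, 9.7.3, Table 3 | SAP 7.1.1 as worded |
|---|---|---|
| Empagliflozin | SU arm, indexed at the SU claim, censored at the empagliflozin claim | Indexed at the empagliflozin claim; not in the SU arm |
| TZD | SU arm, not censored | Indexed at the TZD claim; not in the SU arm |

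The 6-month look-back agrees between the documents and is not at issue.

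**2. The plan's own sample size.** Protocol 9.5 gives 34585.4 per group (Farrington-Manning, ratio R = 1.5, rates 0.0022 in both groups, one-sided 0.05, power 80%, 1:1). The restricted null rates are 0.00264 and 0.00176.

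n = [(1.645·s0 + 0.8416·s1) / |0.0022 − 1.5 × 0.0022|]²

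Here s0² and s1² are the values of p2(1 − p2) + R²·p1(1 − p1) under the null and the alternative. The result is 34585.41, so the figure reproduces; this concern does not alter it. Expected events per group: 34585.4 × 0.0022 = 76.1.

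**3. Illustration of size.** From the documents: AP rate λ = 0.0022 per year. Everything else is assumed:

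- mean on-treatment time 1 year (off-treatment rate 1 per year);
- later-start rate s = 3, 5 or 10% per year, multiplied by k after AP;
- observed time R after SU start = the smaller of a uniform time on 0 to 6.17 years and an exponential disenrolment time with mean 2 years. The mean is prompted by the average history in protocol 9.9.1. Mean R is 1.38 years.

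Formulas:

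- Retained events = E ∫₀ᴿ λ·exp(−(λ+1)t)·exp(−s·t)·exp(−k·s·(R−t)) dt
- Retained person-time = E[exp(−s·R) ∫₀ᴿ exp(−(λ+1)t) dt]
- Apparent HR at true HR 1.0 = λ × person-time / events
- Fraction of SU initiators removed = E[1 − exp(−s·R)] = 4.0 / 6.5 / 12.3%

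| Scenario | HR at s = 3 / 5 / 10% |
|---|---|
| Starts halved after AP (k = 0.5) | 0.98 / 0.97 / 0.94 |
| Unaffected (k = 1) | 1.00 / 1.00 / 1.00 |
| Raised 1.5-fold (k = 1.5) | 1.02 / 1.03 / 1.06 |
| Worst case: AP cases never leave SU (k = 0; needs the unstated fall-back) | 0.96 / 0.94 / 0.88 |
| k = 1, but half the patients have 3 times the AP rate and 3 times the start rate | 1.01 / 1.02 / 1.03 |

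Ranges:

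- Mean disenrolment 1.5 years: halved 0.98 / 0.97 / 0.95, worst 0.97 / 0.95 / 0.90.
- Mean disenrolment 3 years: halved 0.98 / 0.96 / 0.93, worst 0.95 / 0.92 / 0.86.
- Entry confined to the last 2 years (disenrolment mean 2 years): 2 / 4 / 7% removed; halved 0.99 / 0.98 / 0.97, raised 1.01 / 1.02 / 1.03, worst 0.98 / 0.97 / 0.94.

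**4. Effect on the conclusion.** At true HR 1.5 and planned events, SE = √(1/76.1 + 1/114.1) = 0.148. With b the unrounded distortion factor, the chance of wrongly excluding 1.5 is Φ(−ln b/0.148 − z). For b = 0.940 and z = 1.645: Φ(0.418 − 1.645) = 11%.

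| Wrong exclusion, s = 3 / 5 / 10% | Halved | Worst |
|---|---|---|
| One-sided 5%, entry over 6.17 years | 7 / 8 / 11% | 8 / 11 / 21% |
| Two-sided 95% CI (nominal 2.5%), entry over 6.17 years | 3 / 4 / 6% | 5 / 6 / 13% |
| One-sided 5%, entry in last 2 years | 6 / 6 / 8% | 6 / 8 / 11% |
| Two-sided 95% CI, entry in last 2 years | 3 / 3 / 4% | 3 / 4 / 6% |

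In the other direction, power at true HR 1.0 is Φ((ln 1.5 − ln b)/√(2/76.1) − 1.645). With starts raised 1.5-fold (b = 1.019 / 1.032 / 1.060) and entry over 6.17 years, it falls from 80% to 77 / 75 / 69%.

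**The case against.** - **The protocol may leave a gap that the SAP fills.** The index-date definition gives no rule for someone who qualifies for several cohorts over time. Read across all index drugs, it would index on metformin anyone who began metformin in the period and would empty much of the dual cohort. That is a fair reason to read it within a treatment line. Within the dual-therapy comparison, however, the index drugs are empagliflozin and SU, and the earlier SU claim still sets the date.
- **The censoring rules are not wholly contradicted.** Censoring SU patients at any SGLT2 inhibitor still acts on the other drugs of that class, and the add-on permission in SAP 7.1.3 is general. That stands. But the separate rule on adding the within-line comparator is left with almost nothing to act on in the SU arm, and the TZD row of Table 3 is contradicted directly.
- **Figure 1 is not visible and may apply date order.** This stands and limits confidence. If it does, the sentence in the text contradicts the figure and still needs correcting.
- **The effect is usually small, of unknown sign, and rests on assumed inputs.** This stands. At planned events the 95% CI around HR 1.0 runs from about 0.73 to 1.37, wider than any shift in the table of scenarios. The 2-year average in protocol 9.9.1 describes history in the dataset, not enrolment after an SU start. A separate simulation without disenrolment (0.5 to 6 years to study end, start rates up to 20% a year, post-AP multiplier 0 to 2) gave HR factors from 0.51 to 1.94. No single figure should be relied on.

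**Conclusion.** The concern holds for the text as worded, with moderate confidence because Figure 1 cannot be seen. Entry to the SU arm depends on drugs started after SU initiation. That conflicts with the protocol's index-date rule, with its handling of later starts by censoring, and with SAP 7.1.3. Neither the sign nor the size of any bias can be determined from the documents, which give no later-start rates. In the illustration most shifts in the HR are within about 6%. The larger ones need a high start rate together with a fall-back rule that is not stated, or longer observation. It should be corrected before the cohort is relied on: it defines the comparator of the only powered analysis, two independent programmers could build different cohorts from the two documents, and no planned analysis would reveal the effect.

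**What to change.** In SAP 7.1.1 and Figure 1:

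1. For the dual-therapy cohort, set the index date at the earliest qualifying new use of empagliflozin or SU on a metformin background, judged only on information up to that date.
2. Restrict the drug order to starts on the same day.
3. Handle all later starts through protocol Table 3, in both arms.
4. State whether a patient may enter more than one cohort, and whether someone who fails a later drug's criteria remains an SU initiator.
5. Report, per database, the SU initiators, person-years and AP events that the present order would remove.

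If Figure 1 already follows date order, correct the sentence in the text to match it.

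The cost is SAP wording and one re-run of the cohort build on existing data. Patients with an earlier qualifying SU start who had been off SU for at least 6 months before empagliflozin would move to the SU arm. The empagliflozin count therefore falls, by an amount the documents do not give, unless multiple entry is allowed. The SU pool for matching grows.
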